#### **Optional touch-up treatment:**

**Note:** The touch-up treatment may be conducted if an optimal aesthetic correction has not been achieved after repeat-treatment (i.e., at Visit RT1) in the discretion of the treating investigator (see section 6.2.2 for criteria).

The touch-up treatment is optional and must only be conducted if the respective exclusion criteria are not met (see section 6.3.4).

The following assessments must be conducted for the respective subjects:

- Device administration (touch-up treatment)
  - See section 6.2.2 to section 6.2.4 for detailed instructions for injection
  - Document information on injection (see section 6.4.9)
- Record any device deficiencies (see section 14.9)

- Pain assessment (during treatment) using the NPRS by subject immediately (approx.+3 min) after end time of device administration (see section 6.4.14)
- Pain assessment (during recovery from treatment) using the NPRS by subject every 15 min (approx. ±3 min) after end time of the device administration for 60 min post-treatment (see section 6.4.14)
- Perform visual examinations approximately 30 min after device administration (see section 6.4.8)
  - If applicable: Perform basic neurological examination (F.A.S.T) (see section 6.4.9)
- Explain again diary use to the subject and documentation of injection site reactions / symptoms of interest (see section 6.4.19)
- Advise the subject prior to discharge to follow restrictions specified in section 6.3.8.
- Schedule an appointment for telephone visit and the next on-site visit.

## 6.5.13 Visit RT2a - Telephone Visit (24 to 48 hours (±4 hours) after touch-up treatment)

#### Only in case of touch-up treatment at Visit RT2

**Note:** The time of the telephone call has to be documented; it has to be conducted 24 to 48 hours ( $\pm$ 4 hours) after the end of injection at Visit RT2 (see section 6.4.9)

- Ask for any changes in AEs and new AEs (see section 14) including AESIs (see section 14.1)
   In case of an AE including vision changes, neurological issues or an unbearable injection site reaction an unscheduled on-site visit should be performed (see section 6.5.17).
- Ask for changes in concomitant treatments (see section 6.4.7)
- Remind the subject to document injection site reactions / symptoms of interest in the diary (see section 6.4.19)

## 6.5.14 Visit RT2b – Safety follow-up (2 weeks (±3 days) after touch-up treatment)

#### Only in case of touch-up treatment at Visit RT2

- Record any changes in AEs and new AEs (see section 14) including AESIs (see section 14.1)
   In case of an AE including vision changes, neurological issues, or an unbearable injection site reaction an unscheduled on-site visit should be performed (see section 6.5.17).
- Record changes in concomitant treatments (see section 6.4.7)
- Women of child-bearing potential: Urine dipstick pregnancy test (see section 6.4.4)
- Review subject diary regarding injection site reactions / symptoms of interest; confirm review (see section 6.4.19)
- Perform visual examinations (see section 6.4.8) and review respective exclusion criteria (see section 6.3.5)
  - o If applicable: Perform basic neurological examination (F.A.S.T) (see section 6.4.9)

## 6.5.15 Visit RT3 to RT5 - Week 4 to Week 24 (after last injection)

Through the follow-up phase after repeat-treatment the following visits will be performed:

- Visit RT3 Week 4 (± 5 d) after last injection
- Visit RT4 Week 12 (± 7 d) after last injection
- Visit RT5 Week 24 (± 7 d) after last injection

Note: Last injection refers to either

- Visit RT1 for subjects without touch-up treatment, or
- Visit RT2 for subjects with touch-up treatment (i.e., TUP2)

The following assessment will be performed:

Record any new AE or changes of AEs (see section 14) including AESIs (see section 14.1)

- Record changes in concomitant treatments (see section 6.4.7)
- Women of child-bearing potential: Urine dipstick pregnancy test (see section 6.4.4)
- Perform visual examinations (see section 6.4.8)
  - If applicable: Perform basic neurological examination (F.A.S.T) (see section 6.4.9)
- Review subject diary and documentation of injection site reactions / symptoms of interest; confirm review (see section 6.4.19) – only Visit RT3
- Perform body weight measurement (see section 6.4.3)
- MVDSS blinded evaluator at the site (see section 6.4.13)
- NLF-SRS –blinded evaluator at site (see section 6.4.14)
- FACE-QTM Satisfaction with overall outcome of treatment (see section 6.4.17) subject
- FACE- $Q^{TM}$  Satisfaction with cheeks (see section 6.4.18) subject
- Schedule an appointment for the next on-site visit Visits RT3 and RT4 only

## 6.5.16 Early Termination Visit

At Early Termination Visit all attempts should be made to perform the assessments described for

- Visit 9 (SV1) if withdrawn during initial treatment phase (see section 6.5.8)
- Visit SV2 to SV4 if withdrawn during screening phase for repeat-treatment (see section 6.5.9)
- Visit RT5 if withdrawn during repeat-treatment phase (see section 6.5.15)

The following assessments are recommended to be completed at a minimum:

- Record any new AE or changes of AEs (see section 14) including AESIs (see section 14.1)
- Record changes in concomitant treatments (see section 6.4.7)
- Women of child-bearing potential: Urine dipstick pregnancy test (see section 6.4.4)
- Perform visual examinations (see section 6.4.8)
  - If applicable perform neurological examination (F.A.S.T) (see section 6.4.9)
- MVDSS blinded evaluator at the site (see section 6.4.12)

Only in case of Early Termination Visit during initial treatment phase (i.e., prior to Visit 9 (SV1)):

- Perform clinical photography (see section 6.4.11)
- Upload the photos for independent blinded photographic reviewer (MVDSS) (see section 6.4.13) and volumetric change measurement (see section 6.4.12)

#### 6.5.17 Unscheduled Visit

An unscheduled visit may be performed at any time during the study if judged necessary by the treating investigator, such as

- severe or serious injection site reactions
- o clinically significant AE including AESIs (see section 14.1)
- suspected or confirmed pregnancy.

In case the unscheduled visit results in early termination of the subject, the assessments for the Early Termination Visit should be performed (see section 6.5.16). Details of the event are to be recorded in the subject's records and in the eCRF.

## 6.6 Factors that may compromise the outcome

There are no foreseeable factors that may significantly compromise the outcome.

Subject eligibility criteria and prohibition of concomitant treatments and aesthetic procedures that may affect the outcome are carefully defined.

A substantial body weight change during the investigation period could possibly affect the results in individual subjects. This may obscure the effectiveness of the device at individual level. This factor will be controlled by monitoring body weight throughout the investigation (see section 6.3.8).

Beard longer than three-day beard, or excessive facial hair as well as prolonged exposure to sunlight or ultraviolet (UV) radiation and may affect the assessments. Subjects will be advised to avoid and to use daily skin care with UV protection in face throughout the entire clinical investigation (see section 6.3.8).

It is possible that women will prevail in the study population because they still more often seek facial aesthetic procedures than men. This potential gender imbalance will reflect common practice and is not considered relevant since available data on soft tissue fillers do not indicate any gender-related effect on treatment outcomes.

It may also happen that persons of color are enrolled in less numbers. When selecting the study sites, however, care was taken to ensure that adequate numbers of subjects with Fitzpatrick Skin Types (FST) IV, V, or VI will be enrolled to evaluate the safety profile for the subjects with the darkest skin types. To avoid disproportionate enrollment patterns with potential influence on the results FST enrollment levels were implemented (see section 6.3.2). In any case, every effort possible will be taken to enroll males and all Fitzpatrick Skin Types.

Changes in study visit schedules, missed visits, or patient discontinuations may lead to missing information for protocol-specified procedures. The sponsor will implement measurements to prevent an influence on the outcome measures due to COVID-19 pandemic, as appropriate (see section 4.4). However, if changes are unavoidable, specific information will be captured in the subject's source records and in the eCRF that explains the relationship to COVID-19 for missing protocol-specified information. The information will be summarized in the clinical investigation report (see section 8.5) or in a separate study-specific document, as applicable.

## 6.7 Monitoring and Monitoring plan

The conduct of this clinical investigation will be monitored by the sponsor's representative, who will appoint one or more monitors. The extent of monitoring and source data verification will be specified in the Monitoring plan.

Prior to initiation of the clinical investigation at any of the investigation sites, the Monitor will discuss the CIP, the eCRF and other investigation-related documents and forms with the investigator and their staff, and verify that all prerequisites for the initiation are met. No subject should be enrolled into the investigation before this site initiation visit.

During the investigation, further monitoring visits will be performed according to GCP, the applicable standard operating procedures, and local regulations. At each visit the monitor will check the progress of enrolment, will review source data for adherence to the CIP, review eCRFs against source data for completeness, accuracy and consistency, and will also check if the device has been stored, dispensed and accounted for according to respective specifications.

The monitor will inform the investigator or their authorized designee on any error in the eCRF and will ensure that appropriate data corrections or clarifications are made in appropriate manner. In case of any other observed default, the monitor will inform the investigator and, when appropriate, the sponsor as well. The monitor will discuss and agree with the investigator suitable corrective actions and will follow-up their implementation.

Upon completion of the investigation, the monitor will ensure that all investigator's records are accurate and complete, all documents needed for the sponsor's files are retrieved, the remaining investigation supplies, including the device, are disposed of, and that all previously identified issues have been resolved.

The investigator and their institution must permit the monitoring of the investigation and must provide the monitor a direct access to those portions of the subject's source records, which directly concern this clinical investigation. Furthermore, key personnel at the site involved in the investigation must be available to assist the monitor during the monitoring visits.

## 6.8 Audits and inspections

The investigator will permit study related audits, IRB/EC review, and regulatory inspections, providing direct access to source data / documents.

Audits of the clinical investigation may be conducted by the sponsor or external organizations designated by the sponsor to evaluate compliance with the CIP, written procedures, GCP and the applicable regulatory requirements.

A risk-based approach will be used for selection of investigator sites for an audit. The following criteria may be used as a guide for site selection (including but not limited to):

- Study specific requirements.
- Sites with high and/or rapid enrolment.
- Negative outcome from regulatory inspections (e.g. Form FDA 483 issued).
- Level of professional experience of the assigned Site Monitor/CRA.
- Input from other sources (e.g., CROs, CRAs, project team members, centralized Monitoring findings, etc.).
- Previous experience with the investigator and/or site, including, but not limited to:
  - Performance and/or regulatory history
  - o Sites with high volume of clinical studies currently active
  - o Sites with less experience in clinical studies
  - Sites with high incidences of (Serious) Adverse Events (S)AEs)
  - o Sites without or low incidence of SAEs and/or AEs when SAEs and/or AEs are expected
  - Sites with high enrollment and no SAEs/AEs
  - Investigator sites in countries that Croma has not conducted studies previously
  - Frequency of deviations/violations
  - o Sites with a high frequency of CRA turn-over or backlog of monitoring visits.
- Sites that have not been the subject of other audits or inspections (e.g., Co-Visit Audit, Sponsor Site Audits, Regulatory Inspections) within the prior 6 months.
- Sites with an adequate number of enrolled subjects to ensure sufficient data for review during the audit.

A visit may be arranged by the sponsor or sponsor's representative in order to audit the investigation site and the investigation documents, which originate there. The auditor(s) will usually be accompanied by the monitor or the project manager. The investigator will be informed about the outcome of the audit.

In addition, inspections by health authority representatives, including foreign authorities, are possible at any time. The investigator should notify the sponsor and/or sponsor's representative **example**) of any such inspection immediately.

## 6.9 Quality and risk management

The sponsor will implement a system to manage quality throughout all stages of the study process in accordance with GCP, applicable regulations, and sponsor's / CRO's procedures (e.g., written SOPs).

The system implemented will focus on study activities essential to ensure human subject protection and the reliability of study results. The methods used to assure and control the quality of the investigation should be proportionate to the risks inherent in the investigation and the importance of the information collected. All aspects of the study should be operationally feasible and should avoid unnecessary complexity, procedures, and data collection. During Clinical Investigational Plan development processes and data that are critical to ensure human subject protection and the reliability of trial results were identified.

In general, risks should be considered at both the system level (e.g., standard operating procedures, computerized systems, personnel) and clinical trial level (e.g., study design, data collection, informed consent process).

The approach used to reduce risk to an acceptable level should be proportionate to the significance of the risk. Predefined quality tolerance limits will be established, taking into consideration the medical and statistical characteristics of the variables as well as the statistical design of the trial, to identify systematic issues that can impact subject safety or reliability of trial results. Detection of deviations from the predefined quality tolerance limits should trigger an evaluation to determine if action is needed.

Quality management activities must be documented and communicated to those who are involved in or affected by such activities, to facilitate risk review and continual improvement during clinical trial execution.

Details and consequences resulting from the ongoing risk management process are dealt with in the study specific risk management plan filed in the TMF.

# 7 Statistical considerations

Planned statistical analyses are briefly summarized below. Data analyses will be described in detail in the Statistical Analysis Plan (SAP).

## 7.1 Sample size and hypothesis

The primary outcome measures for effectiveness will be evaluated by means of a one-sided two-group Farrington-Manning test for the difference between proportions with the following hypotheses:

- H0:  $pA pB \le -10\%$
- H1: pA pB > 10%

At this, pA is the percent response rate for saypha® VOLUME Lidocaine based on the blinded evaluator's live assessment at Week 24 after last injection of initial treatment phase, while pB is the corresponding response rate for the saypha . Thus, a negative value for this difference means that the response rate of saypha® VOLUME Lidocaine is lower than the response rate for

The non-inferiority margin is -10%.

Further assumptions for sample size calculation:

- Response rate at Week 24 for saypha® VOLUME Lidocaine is 85.6%
- Response rate at Week 24 for the second se
- Randomization ratio 2:1

Based on these assumptions, 437 subjects (saypha® VOLUME Lidocaine: n=291,

 $\alpha$  of 2.5%. Assuming 10% exclusion from PPS results in 486 subjects to be randomized. Adding 6% screen failures yields approximately 516 subjects to be enrolled.

Concerning FAS, it is expected that only very few subjects will be regarded as non-responder due to missing data for the primary effectiveness endpoint. Response rates at Week 24 after last injection of the initial treatment phase may be slightly smaller than assumed above. Due to the increased sample size in the FAS (more than 10% compared to the PPS) it is expected that the power will be adhered as specified above.

Sample size calculation was done using SAS® version 9.4.

Approximately 300 subjects are estimated to qualify for repeat treatment.

## 7.2 Analysed data sets

#### Safety Analysis Set (SAF)

The SAF comprises all subjects who were randomized and received at least one treatment with device (test device or the comparator device). Subjects in the SAF will contribute to the evaluation "as treated" i.e., the subjects' assignment to the treatment group will be based on the device administered.

#### Full Analysis Set (FAS)

The FAS consists of all randomized subjects who received at least one administration of the test device or the comparator device. The statistical evaluation of the FAS will follow the intention-to-treat (ITT) principle and subjects will contribute to the evaluation "as randomized".

#### Per-Protocol Set (PPS):

The PPS is defined as a subset of the subjects in the FAS without major protocol deviation(s) affecting the primary effectiveness endpoint and assessed as 'major excluding from PPS'.

The relevance of protocol deviations will be assessed at the interim and final Data Review Meetings (DRMs). Protocol deviations will be assessed as either "minor" or "major". Major protocol deviations that could directly interfere with analysis of the primary effectiveness endpoint will be further assessed as either 'major *excluding* from PPS' or `major *not* excluding from PPS'. Randomization errors will be considered 'major excluding from PPS'.

The criteria for this assessment will be defined before analysis in Protocol Deviation Manual. Listings will be prepared to assess the eligibility of all subjects during the (i)DRM.

All effectiveness analyses for the initial treatment phase will be conducted using the PPS and the FAS. The effectiveness analysis for the repeat treatment phase will be conducted using the FAS only. Safety analyses will be based on the SAF.

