---------------------------------------------------------------------	---------------------------------------------------------------------------------------------------------------------------------------------------------------------------------------------------------------------------------------------------------------------------------------------------------------------------------------------------------------------------	--	
Source Records	Collection of source documents containing source data.		
Sponsor	Is an individual, company, institution or organization taking responsibility and liability for the initiation and management of a clinical investigation, and arranging the financial setup.		
Subject	Is an individual who is or becomes a participant in a clinical investigation either as a recipient of the test device or the comparator device.		
Treatment (phase) (study-specific definition)	Baseline treatment: Treatment at Visit 2 is defined as "baseline treatment";		
	Touch-up treatment 1: Optional treatment at Visit 3 is defined as "touch-up treatment 1" (TUP1)		
	Initial treatment (phase): Baseline treatment and touch-up treatment together are defined as "initial treatment"; The study phase between Baseline visit and Visit 9 (SV1) is defined as initial treatment phase.		
	For initial treatment either saypha® VOLUME Lidocaine (test device) or the comparator device and the subject are administered (according to randomization of the subject)		
	Repeat-treatment (phase): Optional treatment (with saypha® VOLUME Lidocaine only) at Visit RT1 is defined as "repeat-treatment". The study phase beginning with repeat-treatment at Visit RT1 and up to Visit RT5 is defined as repeat-treatment phase.		
	Touch-up treatment 2: Optional treatment at Visit RT2 is defined as "touch-up treatment 2" (TUP2)		
	For repeat-treatment only saypha® VOLUME Lidocaine (test device) is administered.		
Treating (unblinded) investigator (study-specific definition)	Responsible for all study related assessments and procedures (except those allocated to the blinded evaluator at the site and the central independent blinded photographic reviewer).		
Trial Master File (TMF)	Binder(s) maintained at the sponsor's (CRO's) office containing all regulatory and study specific documents including the essential documents according to the ISO-GCP Guideline.		

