# 5.3.2 Primary effectiveness endpoint

The effectiveness of the investigational device will be evaluated using the following primary endpoint:

 The percentage of responders on the 5-point MVDSS, based on *the blinded evaluator's live* assessment at Week 24 after last injection of initial treatment phase compared to the pretreatment score at Baseline visit

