#### MVDSS, NLF-SRS and Volumetric Change measurement

- The percentage of responders on the 5-point MVDSS, based on the *blinded evaluator's live* assessment at Week 4, 8, 16, 36, and 48 after last injection of initial treatment phase compared to the score at Baseline visit.
- The percentage of responders on the 5-point MVDSS, based on the *independent blinded photographic reviewer's* assessment by using Baseline photographs at Week 4, 8, 16, 24, 36 and 48 after last injection of initial treatment phase compared to the score at Baseline visit
- Mean change in midface volume deficit measured on the 5-point MVDSS and based on the **blinded evaluator's live** assessment at Week 4, 8, 16, 24, 36 and 48 after last injection of initial treatment phase compared to the score at Baseline visit
- Mean change in midface volume deficit as measured by *volumetric change measurement* by using 3D digital photographic images at Week 4, 8, 16, 24, 36 and 48 after last injection of initial treatment phase compared to Baseline visit
- Shift from baseline (Baseline visit) in nasolabial folds measured by NLF-SRS based on the blinded evaluator's live assessment at Week 4, 8, 16, 24, 36, and 48 after last injection of initial treatment phase

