In addition, at least the following main secondary effectiveness endpoints will be compared between the treatment groups by means of 95% confidence intervals for the differences in

- proportion of subjects with response on the MVDSS as assessed by the blinded evaluator at the site
- proportion of subjects with response on the MVDSS as assessed by the independent blinded photographic reviewer
- mean change in midface volume deficit measured on the 5-point MVDSS and based on the blinded evaluator's live assessment
- proportion of subjects with global aesthetic improvement (in modified GAIS) as assessed by the subject
- proportion of subjects with global aesthetic improvement (in modified GAIS) as assessed by the blinded evaluator

This will be done for each time of assessment during follow-up for initial treatment.

The resulting 95% confidence intervals for proportions will be presented in forest plots and the boundaries of the confidence intervals evaluated with respect to their clinical relevance in an exploratory manner.

The investigational device during repeat-treatment phase (saypha® VOLUME Lidocaine) will be evaluated descriptively using the following other endpoints:

- The percentage of responders on the 5-point MVDSS, based on the *blinded evaluator's live* assessment at Week 4, 12 and 24 after last injection of repeat-treatment phase compared to the score at Visit RT1
- Mean change in midface volume deficit measured on the 5-point MVDSS and based on the blinded evaluator's live assessment at Week 4, 12, and 24 after last injection of repeat-treatment phase compared to the score at Visit RT1
- Shift from baseline (Visit RT1) in NLF-SRS based on the blinded evaluator's live assessment at Week 4, 12 and 24 after last injection during repeat-treatment phase
- The extent of subject's satisfaction with overall treatment outcome at Week 4, 12 and 24 after last injection of repeat-treatment phase as assessed by the subject using the Face-QTM Questionnaire "Satisfaction with Outcome"

- The extent of subject's appearance appraisal at Week 4, 12 and 24 after last injection of repeattreatment phase as assessed by the FACE-QTM questionnaire "Satisfaction with Cheeks" compared to the score at Visit RT1
- Subject evaluation of pain after each treatment (repeat and touch-up-treatment) on an 11-point scale, where 0 is no pain and 10 is the worst pain imaginable

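### PPS membership is decided by the Week 24 endpoint alone, yet the same set serves Weeks 36 and 48, so a prohibited midface procedure after Week 24 is no ground for exclusion there

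*Protocol*

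**What the plan says.** Section 7.2 defines the set: "The PPS is defined as a subset of the subjects in the FAS without major protocol deviation(s) affecting the primary effectiveness endpoint". It also says which deviations are considered for exclusion at all: "Major protocol deviations that could directly interfere with analysis of the primary effectiveness endpoint will be further assessed as either" excluding or not excluding from the PPS. The primary endpoint (5.3.2) is MVDSS response "at Week 24 after last injection of initial treatment phase compared to the pretreatment score at Baseline visit".

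The same section then fixes where the set is used: "All effectiveness analyses for the initial treatment phase will be conducted using the PPS and the FAS". Section 7.3 repeats this for the primary and secondary endpoints. The Glossary gives the length of the phase: "The study phase between Baseline visit and Visit 9 (SV1) is defined as initial treatment phase", and Visit 9 is Week 48. Section 5.3.3.1 lists MVDSS response by live "assessment at Week 4, 8, 16, 36, and 48 after last injection of initial treatment phase compared to the score at Baseline visit", and also has MVDSS mean change, volumetric change and GAIS at Weeks 36 and 48. For the main secondary endpoints, 7.3.7 plans between-group 95% confidence intervals: "This will be done for each time of assessment during follow-up for initial treatment".

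Four other provisions bear on the point:
- 6.3.9 prohibits other fillers and listed midface procedures throughout the investigation.
- 6.3.6 lists additional aesthetic correction among the reasons for which a subject may, not must, be withdrawn.
- The sensitivity rule in 7.3.7 that may count users of prohibited treatment as non-responders covers use before Week 24, for the primary endpoint, on the FAS.
- Apart from the primary endpoint, 7.5 allows no imputation and analyses data as recorded.

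**The concern.** A per-protocol result at a visit should describe subjects whose outcome at that visit was not altered by a major deviation. Here membership is settled by one visit and applied to six. The mismatch falls on the two visits after Week 24. Sections 2.1 and 4.1 anticipate an effect lasting up to nine months (about 39 weeks), so Weeks 36 and 48 are when response may be waning and a subject might seek correction elsewhere. A face corrected with another product can then count as a response to the study device.

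At stake is the reading of the exploratory Week 36 and 48 comparisons, whose interval boundaries 7.3.7 says will be judged for clinical relevance.

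**Working it through.** **Step 1: the text.** A score recorded at the Week 24 visit cannot be changed by a procedure performed afterwards. Such a procedure therefore cannot interfere with analysis of the primary endpoint and never reaches the excluding/not-excluding assessment in 7.2. Sections 7.2 and 7.3 still apply the set to Weeks 36 and 48.

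**Step 2: does another provision catch it?**
- Withdrawal under 6.3.6 may, but is discretionary, and an early-termination visit in the initial phase still seeks the Visit 9 assessments, including MVDSS (6.5.16).
- The 7.3.7 sensitivity rule stops at Week 24.
- The FAS keeps the score as observed (7.5).

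No stated analysis sets these assessments aside.

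**Step 3: the plan's own figure.** The protocol gives no number for this point. Its PPS allowance reproduces: 437/(1 - 0.10) = 485.6, hence 486 randomized. Nothing below changes it.

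**Step 4: illustration.** Assumed inputs, none from the protocol: true Week 48 response of p = 50% (test) and 60% (comparator); a share q of the waned subjects (1-p) has outside correction; all of these score as responders.

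- As planned: observed rate = p + (1-p)q. With equal q the difference is (pA - pB)(1-q).
- Post-procedure assessments left out: rate = p/[p + (1-p)(1-q)].
- Post-procedure subjects counted as non-responders: rate = p, because in this model only waned subjects are corrected.

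| q test / comparator | As planned | Left out | Counted as non-response |
|---|---|---|---|
| 10% / 10% | 55.0 v 64.0 (-9.0) | 52.6 v 62.5 (-9.9) | 50 v 60 (-10) |
| 20% / 20% | 60.0 v 68.0 (-8.0) | 55.6 v 65.2 (-9.7) | 50 v 60 (-10) |
| 20% / 10% | 60.0 v 64.0 (-4.0) | 55.6 v 62.5 (-6.9) | 50 v 60 (-10) |
| 10% / 20% | 55.0 v 68.0 (-13.0) | 52.6 v 65.2 (-12.6) | 50 v 60 (-10) |

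For example, 0.50 + 0.50 × 0.10 = 0.55; 0.50/(0.50 + 0.50 × 0.90) = 0.526.

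**Step 5: scale.** With 291 test and 437 - 291 = 146 comparator subjects, q = 10% means 0.10 × 0.50 × 291 = about 15 and 0.10 × 0.40 × 146 = about 6 subjects. The standard error of the difference is sqrt(0.25/291 + 0.24/146) = 0.050, so the 95% half-width is about 9.8 points. With equal q the shift of 1 to 2 points is small beside that; with unequal q it need not be.

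**The case against.** The strongest defence is that the choice was deliberate. Amendment 5 (19.5) narrowed the PPS so as not to lose subjects whose deviations leave the Week 24 assessment untouched, and one PPS anchored to the primary endpoint is a common convention. The reason holds for Week 24. It says nothing about Weeks 36 and 48, for which the same amendment kept the set in use.

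Second, all secondary endpoints are exploratory, and 7.3.1 names only SAF and FAS tables for the interim analysis. This stands as a limit on importance. It does not cancel the PPS use stated in 7.2 and 7.3.

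Third, the Protocol Deviation Manual and the SAP are not at hand and may add a rule. They may, but 7.2 states a gate that such a rule would have to override, and 7.7 asks for a protocol amendment where a change affects the effectiveness analysis.

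Fourth, leaving out post-procedure assessments removes mainly waned subjects and still overstates response. This stands, as the third column of the table shows, and is why exclusion alone is not enough.

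A reader might go further and infer any of the following, which the documents do not support:
- Every such subject stays in the late results. The investigator may withdraw the subject, enrolment requires willingness to abstain (6.3.3.1), and non-study filler or listed midface procedures in the initial phase bar repeat-treatment (6.3.5.2), which discourages them.
- Durability is overstated and the device difference pulled toward zero. No rate of outside correction is given, and unequal use can move the difference either way.
- A subject excluded for a deviation at, say, Week 20 loses the Week 4 to 16 data. They leave the PPS but remain in the FAS, which is analysed alongside.
- Section 7.3.7 itself assigns the PPS to the late visits. It names the PPS only for the primary endpoint; the assignment comes from 7.2 and 7.3.

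**Conclusion.** The point holds as a mismatch between how the PPS is defined and where it is used. A prohibited midface procedure after the Week 24 visit is not a ground for exclusion from the Week 36 and 48 PPS results, and no other stated analysis addresses it. The Week 24 non-inferiority decision, the sample size and the power are untouched. The effect on the late comparisons cannot be sized from the protocol. Under the assumed rates and equal q of 10% to 20% it is 1 to 2 points toward zero. With q differing between arms over the same range, the apparent difference runs from -4 to -13 points against a true -10. These figures rest on assumed response rates, assumed q, and every corrected subject scoring as a responder. The change is worth making because it is cheap, not because a trial conclusion depends on it.

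**What to change.** Keep the Week 24 PPS exactly as defined. Add to 7.2 that, for every other initial-phase visit, PPS inclusion is visit-specific: assessments made after a deviation of a type rated as excluding from the PPS are left out, and those made before it are kept.

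For the responder endpoints, extend the 7.3.7 sensitivity rule to Weeks 36 and 48: subjects with a prohibited midface procedure before the visit are counted as non-responders at that visit. This addresses the selection that exclusion leaves behind. It is conservative for anyone who was still a responder when the procedure took place.

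No new data are needed: procedures are recorded to the end of study (6.4.7) and deviations with their dates (section 10). The cost is one rule, a visit-level flag, a PPS denominator that varies by visit, and one extra sensitivity table.
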